### Appendix 1.9. CHAQ Responses

COPYRIGHTED MATERIAL

090177e19fc85b7f\Approved\Approved On: 29-Jan-2024 08:13 (GMT)

COPYRIGHTED MATERIAL

090177e19fc85b7f\Approved\Approved On: 29-Jan-2024 08:13 (GMT)

COPYRIGHTED MATERIAL

#### **Appendix 1.10. ERA: Tender Enthesal Assessment, Modified Schober's Test, Overall Back Pain and Nocturnal Back Pain Responses**

##### Tender Enthesal Assessment

Following anterior/posterior and left/right joint assessment, the investigator will enter one of the following codes for each enthesal on the appropriate CRF. Palpation should be performed per standard practice (e.g., using fingertips) for this assessment.

*Y = Any tenderness upon firm palpation over the indicated enthesal*

*N = No tenderness upon firm palpation over the indicated enthesal*

Number of joints with any tenderness will be counted for the report of Tender Enthesal Assessment.

Modified Schober's Test (Macrae 1969, Moll 1971)

With the subject standing erect and with feet together, a line joining the posterior superior iliac spines (the dimples of Venus) is used as a landmark for the lumbosacral junction. A mark is made 5 cm below and 10 cm above the lumbosacral junction. With the subject in maximum forward flexion with the knees straight, the investigator will measure the distance between the two marks in centimeters. The full measurement between the two lines will be recorded to the nearest tenth of a centimeter (e.g., 15.2 cm) on the appropriate CRF.

[figure not shown]
Overall Back Pain and Nocturnal Back Pain

Overall back pain (at any time) and nocturnal back pain will be measured on a 21-circle visual analog scale (VAS).

[figure not shown]
The parent/legal guardian/subject (if at least 14 years of age and able to complete correctly and consistently) will be asked to fill one circle on the scale shown below in response to the following questions:

Overall Back Pain (Please fill a circle)

What is the amount of back pain at any time that your child experienced in the past week?

Nocturnal Back Pain (Please fill a circle) What is the amount of back pain at night that your child experienced in the past week?

**Appendix 1.11. PsA: Body Surface Area (BSA) and Physician's Global Assessment (PGA) of Psoriasis**

Subjects with psoriatic arthritis (PsA) will undergo additional efficacy assessments, including assessment of body surface area (BSA) affected by Psoriasis and Physician's Global Assessment (PGA) of psoriasis (Horneff 2014).

Body Surface Area (BSA)

BSA will be measured as the percentage of BSA affected by psoriasis using the palm method; the subject's palm will be used for the calculation.

One (1) of the subject's palm to PIP and thumb equals 1% of BSA.

Head and Neck = 10% (10 palms)

Upper extremities = 20% (20 palms)

Trunk (axillae and groin) = 30% (30 palms)

Lower extremities (buttocks) = 40% (40 palms)

Total BSA = 100% (100 palms)

Based on the above, the Physician's Assessment of Total BSA affected by psoriasis will be estimated using the following formula:

Region of the Body	Number of Palms Within the Region Affected by Psoriasis
Head and Neck	
Upper extremities	
Trunk (including the axillae and groin)	
Lower extremities (including the buttocks)	
Physician's Assessment of Total BSA Affected by Psoriasis (addition of the individual regions):	%

Physician's Global Assessment (PGA) of Psoriasis

The PGA of psoriasis is used to determine the subject's psoriasis lesions overall at a given time point. Overall lesions are graded for induration, erythema, and scaling based on the scales below. The sum of the 3 scales is then divided by 3 to obtain the final PGA of psoriasis score.

Please circle one response each for induration, erythema, and scaling:	
Induration (I) (averaged over all lesions): 0 = no evidence of plaque elevation 1 = minimal plaque elevation - 0.5 mm 2 = mild plaque elevation - 1 mm 3 = moderate plaque elevation - 1.5 mm 4 = marked plaque elevation - 2 mm 5 = severe plaque elevation - 2.5 mm or more	Erythema (E) (averaged over all lesions): 0 = no evidence of erythema, hyper pigmentation may be present 1 = faint erythema 2 = light red coloration 3 = moderate red coloration 4 = bright red coloration 5 = dusky to deep red coloration
Scaling (S) (averaged over all lesions): 0 = no evidence of scaling 1 = minimal; occasional fine scale over less than 5% of the lesion 2 = mild; fine scale predominates 3 = moderate; course scale predominates 4 = marked; thick, non-tenacious scale predominates 5 = severe; very thick tenacious scale predominates	

Add I + E + S = \_\_\_\_\_ / 3 = \_\_\_\_\_ (Total Average)

- ☐ (0) Clear, except for residual discoloration
- ☐ (1) Majority of lesions have individual scores for  $[(I + E + S) / 3]$  that **averages 1**
- ☐ (2) Majority of lesions have individual scores for  $[(I + E + S) / 3]$  that **averages 2**
- ☐ (3) Majority of lesions have individual scores for  $[(I + E + S) / 3]$  that **averages 3**
- ☐ (4) Majority of lesions have individual scores for  $[(I + E + S) / 3]$  that **averages 4**
- ☐ (5) Majority of lesions have individual scores for  $[(I + E + S) / 3]$  that **averages 5**

Note: Scores should be rounded to the nearest whole number:

If total average  $\leq 1.49$ , score = 1

If total average  $\geq 1.50$ , score = 2

**Appendix 1.12. Definition and Use of Visit Windows in Reporting**

Visit windows will be used for efficacy variables, and for any safety displays that display by visit. If more than one observation from the same subject falls into the same visit window, the value closest to the targeted day will be used as the observation for that visit. If there are two days having the same distance from target day, the earlier day will be used. All observations will, however, be included in the listings.

Visit Label	Target Day	Definition [Day window]
Baseline	Day 1	Day 1
Month 1	Day 30	Days 2-60
Month 3	Day 90	Days 61-135
Month 6	Day 180	Days 136-225
Month 9	Day 270	Days 226-317
Month 12	Day 360+5=365	Days 318-410
Month 15	Day 450+5=455	Days 411-500
Month 18	Day 540+5=545	Days 501-590
Month 21	Day 630+5=635	Days 591-683
Month 24	Day 720+10=730	Days 684-775
Month 27	Day 810+10=820	Days 776-865
Month 30	Day 900+10=910	Days 866-955
Month 33	Day 990+10=1000	Days 956-1048
Month 36	Day 1080+15=1095	Days 1048-1140
Month 39	Day 1170+15=1185	Days 1141-1230
Month 42	Day 1260+15=1275	Days 1231-1320
Month 45	Day 1350+15=1365	Days 1321-1413
Month 48	Day 1440+20=1460	Days 1414-1505
Month 51	Day 1530+20=1550	Days 1506-1595
Month 54	Day 1620+20=1640	Days 1596-1685
Month 57	Day 1710+20=1730	Days 1686-1778
Month 60	Day 1800+25=1825	Days 1779-1870
Month 63	Day 1890+25=1915	Days 1871-1960

Visit Label	Target Day	Definition [Day window]
Month 66	Day 1980+25=2005	Days 1961-2050
Month 69	Day 2070+25=2095	Days 2051-2143
Month 72	Day 2160+30=2190	Days 2144-2235
Month 75	Day 2250+30=2280	Days 2236-2325
Month 78	Day 2340+30=2370	Days 2326-2415
Month 81	Day 2430+30=2460	Days 2416-2508
Month 84	Day 2520+35=2555	Days 2509-2600
Month 87	Day 2610+35=2645	Days 2601-2690
Month 90	Day 2700+35=2735	Days 2691-2780
Month 93	Day 2790+35=2825	Days 2781-2873
Month 96	Day 2880+40=2920	Days 2874-2965
Month 99	Day 2970+40=3010	Days 2966-3055
Month 102	Day 3060+40=3100	Days 3056-3145
Month 105	Day 3150+40=3190	Days 3146-3238
Month 108	Day 3240+45=3285	Days 3239-3330
Month 111	Day 3330+45=3375	Days 3331-3420
Month 114	Day 3420+45=3465	Days 3421-3510
Month 117	Day 3510+45=3555	Days 3511-3603
Month 120 a	Day 3600+50=3650	≥ Days 3604

a: Additional visits may be added depending on the actual total duration of the study.

For the summary of Tanner Stage, the following visit windows will be used.

Visit Label	Target Day	Definition [Day window]
Baseline	Day 1	Day 1
Month 12	Day $360+5=365$	Days 2-547
Month 24	Day $720+10=730$	Days 548-912
Month 36	Day $1080+15=1095$	Days 913-1277
Month 48	Day $1440+20=1460$	Days 1278-1642
Month 60	Day $1800+25=1825$	Days 1643-2007
Month 72	Day $2160+30=2190$	Days 2008-2372
Month 84	Day $2520+35=2555$	Days 2373-2737
Month 96	Day $2880+40=2920$	Days 2738-3102
Month 108	Day $3240+45=3285$	Days 3103-3467
Month 120 a	Day $3600+50=3650$	$\geq$ Days 3468

a: Additional visits may be added depending on the actual total duration of the study.

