6. Pharmacokinetic (PK) blood samples will be collected at Month 12 and at approximately yearly intervals thereafter up to Month 36 (ie, Month 12, Month 24, Month 36). Samples will be collected at pre-dose and 0.5 hr (time window: 0.25-0.75 hr) and 2 hr (time window: 1.75-2.5 hr) post-dose. PK samples will be collected at the End of study/Early Termination Visit up to Month 36; this collection may not be possible or feasible if drug has been discontinued prior to this visit; a comment should be included in the applicable PK CRF page. The subject and parent/legal guardian will be instructed that the subject should not take the morning dose until after the pre dose PK sample is collected. See [Section 7.4](#) for details regarding PK sampling. PK blood samples will not be collected from participants in India.
7. End of Study (EOS) Visit for the qualifying/index study.
8. Visits will occur every 3 months after the Month 1 visit and throughout the study. Visit windows: Months 1 and 3 Visits (± 5 days); Months 6 and subsequent visits (± 10 days).
9. Collected in all subjects who enroll more than 14 days after their EOS Visit for their qualifying/index study. Hepatitis B: HBs Ag and HBc Ab are tested in all subjects who undergo a Screening visit. HBs Ab is analyzed in subjects who test negative for HBsAg but positive for HBcAb. If when tested, the HBsAb test is negative (surface antibody negative), the subject will be excluded from the study. Hepatitis B testing will not be performed in subjects determined to be HBs Ab positive in their qualifying study. Hepatitis C: HCV RNA tested in case a positive HCV Ab result is obtained. To conserve blood volume at screening, HCV RNA sample collection may be deferred and collected only if required to confirm eligibility based on the HCV Ab results. See [Section 7.2.9](#).
10. **Applicable to Canadian Investigator Sites Only:** Excluding the Month 1 visit, calculate the subject's ACR30 response (see [Section 7.1.6.1](#)) at each visit. Subjects with less than an ACR30 response at 2 consecutive visits, beginning with the Month 3 visit and anytime thereafter, should be discontinued from study treatment, unless in the opinion of the Investigator, it is in the subject's best interest to continue receiving tofacitinib (to be determined on a case-by-case basis and in consultation with the Sponsor).

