- Safety laboratory testing (chemistry, hematology, urinalysis), including urine pregnancy testing (β-hCG) for females of child-bearing potential.
- Confirm highly effective contraception is being used.
- CRP.
- ESR determination (Westergren method).
- Assess investigational product dosing compliance.
- Dispense/collect study medication.

sJIA subjects ONLY:

- Assessment of JIA-associated fever: Fever is defined as temperature $>38^{\circ}\text{C}/100.4^{\circ}\text{F}$. Refer to [Section 7.1.10.1](#) for details.
- MAS diagnosis: Only if subject has fever and Macrophage Activation Syndrome (MAS) is suspected: obtain blood samples to evaluate ferritin, platelets, triglycerides and fibrinogen levels. Refer to [Section 7.2.9](#) for details regarding these blood sample collections.
- Assess extra-articular sJIA manifestations: rash, serositis, splenomegaly, hepatomegaly, or generalized lymphadenopathy attributable to sJIA.

ERA subjects ONLY (Months 66, 78, 90, 102, and 114):

- Tender Enthesal Assessment.
- Modified Schober's Test.
- Overall Back Pain.
- Nocturnal Back Pain Assessment.

PsA subjects ONLY (Months 66, 78, 90, 102, and 114):

- Body surface area (BSA) with psoriasis rash.
- Physician's Global Assessment (PGA) for psoriasis.

Applicable to Canadian Investigator Sites Only: Calculate the subject's ACR30 response (see [Section 7.1.6.1](#)) at each visit. Subjects with less than an ACR30 response for 2 consecutive visits, beginning with the Month 3 visit and anytime thereafter, should be discontinued from study treatment, unless, in the opinion of the Investigator, it is in the subject's best interest to continue receiving tofacitinib (to be determined on a case-by-case basis and in consultation with the Sponsor).

6.2.4. Years 6-10: Month 72, 84, 96, 108, 120 Visits (Visit Window ± 10 Days)

The following procedures and assessments will be performed:

- AE assessment.
- Risk factor check for venous thromboembolism (see [Section 7.2.10](#)).
- Document concomitant medications (ongoing or started since previous visit).
- Childhood Health Assessment Questionnaire (CHAQ).

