## 2.2. Study Design

This is a Phase 2/3, long term, open-label, follow-up study. Subjects will have previously participated in qualifying/index study in the tofacitinib JIA program. Those who have already completed such participation and enroll outside the 14-day window following completion of the End of Study (EOS) Visit of the qualifying/index study will participate in a Screening Visit to determine eligibility. A Baseline Visit will then occur within 28 days after the Screening Visit. For subjects who are completing participation in a qualifying study of tofacitinib and enrolling on the same day of the EOS Visit of the qualifying/index study, the EOS Visit of the qualifying/index study can be combined with the Screening and Baseline Visits for this study. The subjects who enroll within the 14-day window following completion of the EOS Visit of the qualifying/index study will participate in a combined Screening and Baseline Visit for this study. After the Baseline Visit, visits will occur at 1 month (1 month=30 days) and 3 months, then every 3 months thereafter as long as the subject remains in the study.

Approximately 340 participants are projected to enroll into this open label extension study after completing a qualifying/index study (i.e., A3921103, A3921104 or A3921165) in the JIA program.

For subjects who entered this study from the A3921103 and A3921104 qualifying/index studies, their participation in this study ends after the first global marketing approval of tofacitinib for the treatment of polyarticular course Juvenile Idiopathic Arthritis (pJIA) in any country.

This study will end once the last subject, and all other subjects, who entered from study A3921165 have completed approximately 1 year in this study, or after the first marketing approval of tofacitinib for the treatment of systemic JIA, whichever comes first.

The total duration of an individual subject's participation may vary depending upon when they entered the trial.

**Applicable to Canadian Investigator Sites Only:** The duration of subject participation will be restricted to 3 years, unless, in the Investigator's opinion, it is in the subject's best interest to continue receiving tofacitinib (to be determined on a case-by-case basis and in consultation with the Sponsor).

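### SAP visit windows follow 365-day years while visits are scheduled on 30-day months, so some late on-schedule visits take the wrong label and Month 120 is left empty; Day 1048 also sits in two windows.

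*SAP*

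**What the plan says.** **Schedule.** Protocol Section 3 and SAP Section 2.2 give the same rule: "After the Baseline Visit, visits will occur at 1 month (1 month=30 days) and 3 months, then every 3 months thereafter". Footnote 8 to the protocol's Schedule of Activities sets the tolerance: "Months 6 and subsequent visits (± 10 days"; for Months 1 and 3 it is ±5 days. The schedule runs to Year 10, as in the protocol heading "6.2.4. Years 6-10: Month 72, 84, 96, 108, 120 Visits (Visit Window ± 10 Days".

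**Analysis windows.** SAP Appendix 1.12 starts from the 30-day count and adds 5 days for each completed year. Month 108 is "Day 3240+45=3285" with window "Days 3239-3330", and Month 120 is "Day 3600+50=3650" with window Day 3604 onward. The windows apply to efficacy variables and to by-visit safety displays. If two observations share a window, the one nearer the target is used; on a tie, the earlier one is used. Listings keep everything.

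**Overlap.** In the same table Month 33 is Days 956-1048 and Month 36 is "Days 1048-1140".

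**The concern.** Two month lengths are in use. Visits are booked on one and assigned to a label on the other, and the gap grows by 5 days a year. Successive visits are 90 days apart, so once the gap approaches 45 days an on-schedule visit can fall in the previous visit's window. Two visits can then compete for one label, and a later label gets no data. At stake are the labels and counts in the by-visit efficacy and safety tables at the longest follow-up, in a study whose purpose is long-term safety and persistence of effect.

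**Working it through.** **Inputs.** Month length of 30 days (Protocol Section 3, SAP Section 2.2); tolerance ±10 days from Month 6 (Schedule of Activities, footnote 8); targets, windows and selection rules (SAP Appendix 1.12).

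**Reproducing the SAP's targets.** Target = 30m + 5 × floor(m/12) gives all 41 post-baseline targets as printed. For example, Month 108 is 3240 + 5 × 9 = 3285 and Month 120 is 3600 + 5 × 10 = 3650. The window edges are midpoints between neighbouring targets, for example (3285 + 3375)/2 = 3330.

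**Day numbering.** The target column uses Day 30m as its base, but the table also calls baseline Day 1, which would put a visit 30m days later on Day 30m+1. The SAP does not settle this, so both are shown.

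**Allowed days (21 per visit) outside the visit's own window:**

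| Visit | Day 30m | Day 30m+1 |
|---|---|---|
| Through Month 84 | 0 | 0 |
| Months 87, 90, 93 | 1 | 0 |
| Month 96 | 4 | 3 |
| Months 99, 102, 105 | 6 | 5 |
| Month 108 | 9 | 8 |
| Months 111, 114, 117 | 11 | 10 |
| Month 120 | 14 | 13 |

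Example, Month 120 with Day 30m: the allowed days are 3590-3610 and the window opens on Day 3604, so Days 3590-3603 (14 days) are outside. (At Months 1 and 3 the tolerance gives 11 allowed days, none outside.)

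**A subject exactly on schedule, Day 30m.**
- Month 111 (Day 3330) is labelled Month 108, Month 114 (3420) Month 111, Month 117 (3510) Month 114, and Month 120 (3600) Month 117.
- The Month 108 window holds Days 3240 and 3330. Distances from target are 3285 − 3240 = 45 and 3330 − 3285 = 45. The tie rule keeps Day 3240, so the Month 111 visit leaves the by-visit summaries.
- Month 120 is empty.

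**The same subject, Day 30m+1.**
- Months 111 (3331), 114 (3421) and 117 (3511) fall in their own windows.
- Month 120 (3601) falls in the Month 117 window, target 3555. Distances are 3555 − 3511 = 44 and 3601 − 3555 = 46. Day 3511 is kept, so the Month 120 visit leaves the summaries.
- Month 120 is again empty.

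**Day 1048.** The midpoint of the Month 33 and Month 36 targets is (1000 + 1095)/2 = 1047.5. Later year-end rows round up and start the next window a day later (683/684, 1413/1414, 1778/1779). Month 36 should start on Day 1049 on that pattern. No allowed scheduled visit lands on Day 1048 (Month 33: Days 980-1000; Month 36: Days 1070-1090), so only unscheduled or out-of-window assessments are touched.

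**Tanner windows.** Each annual Tanner window contains its 30-day visit ±10 days. For Month 120, Days 3590-3610 lie inside the window from Day 3468.

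**The case against.** The strongest reply is that the 5-day increments are deliberate. They convert 30-day months to calendar years, and the protocol itself speaks of study years and annual assessments. If sites booked by calendar month, the printed windows label every on-time visit correctly through Month 120. That stands as a limit on the concern. It does not remove it, because both documents state a 30-day month and neither tells sites to book by calendar.

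The second reply is reach, and it largely stands. Participation from A3921103 and A3921104 ends after the first pJIA approval, which Protocol Section 1.1 already reports. If A3921104 roll-over began no earlier than Amendment 4 (03 April 2015), Day 2600, the earliest day that can be mislabelled, is mid-May 2022. If entry from A3921165 began with Amendment 7 (10 August 2017), Day 3330 is in September 2026, while the study ends about a year after the last such entry, or earlier on sJIA approval. The main exposed group would then be A3921103 roll-overs, and that study dosed 26 subjects. These dates are inferences; the documents give no count of subjects at these visits.

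Two stronger readings are tempting and not supported:
- A reader might infer that the Month 111 visit is always lost and that Months 114-120 always shift back one label. That holds only with Day 30m numbering.
- A reader might infer that data are discarded or that the main safety results are distorted. Listings keep all observations, and the incidence rates in SAP Section 6.6 use dosing, event and contact dates, not visit windows.

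**Conclusion.** The mismatch is real on the documents' own rules, and its importance is minor. If sites follow the stated 30-day schedule, one on-time late visit is left out of the by-visit summaries and Month 120 is empty, whichever day numbering is used. Which visit is lost, and how many labels move (four with Day 30m, one with Day 30m+1), depends on the numbering. The result assumes subjects followed long enough to reach the affected visits, probably few. The Day 1048 overlap needs no assumption: it is a one-day table error that prevents unique assignment of that day.

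**What to change.** Label scheduled visits by their nominal CRF visit and use day windows only for unscheduled and early-termination assessments. This is right under either 30-day or calendar booking. Because the windows remain in use for those assessments, the overlap must be repaired separately: change Month 36 to Days 1049-1140.

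If day windows are kept for scheduled visits, check first how sites actually booked, then base the targets on the same month length the protocol uses for scheduling, and state which day number a Month m visit has. Re-targeting to Day 30m without that check could move the problem. With windows of 30m − 44 to 30m + 45, Month 102 would end on Day 3060 + 45 = 3105, and a calendar-booked Month 102 visit on about Day 3106 would be labelled Month 105.

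The cost is one SAP table and its programming lookup, before database release. No endpoint or study procedure changes.

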### Appendix 1.13. Protocol Deviations

While protocol deviations will be listed in the clinical study report, none will form part of statistical analyses since no per protocol analyses are planned.

**Appendix 2. List of Abbreviations**

Abbreviation	Term
ACR	American College of Rheumatology
AE	adverse event
ALT	alanine aminotransferase
AST	aspartate aminotransferase
ATE	arterial thromboembolism
BSA	body surface area
CFB	change from baseline
CHAQ	Childhood Health Assessment Questionnaire
CI	confidence interval
CL/F	oral clearance
COVID-19	corona virus disease 2019
CRF	case report form
CRP	C-reactive protein
DILI	drug induced liver injury
DMARD	disease modifying antirheumatic drug
DVT	deep vein thrombosis
EMA	European Medicines Agency
EOS	end of study
ERA	enthesitis-related arthritis
ESR	erythrocyte sedimentation rate
EU VHP	EU Voluntary Harmonisation Procedure
FAS	full analysis set
FDA	Food and Drug Administration (United States)
GCP	Good Clinical Practice
GI	gastrointestinal
HZ	herpes zoster
IFN	interferon
IL	interleukin
ILD	interstitial lung disease
IR	incidence rate
JADAS	Juvenile Arthritis Disease Activity Score
JAK	janus kinase
JIA	juvenile idiopathic arthritis
LDL	low-density lipoprotein
MACE	major adverse cardiovascular event
MAS	macrophage activation syndrome
MCP	metacarpophalangeal
MedDRA	Medical Dictionary for Regulatory Activities
MTX	methotrexate
NMSC	nonmelanoma skin cancer
OI	opportunistic infection
PD	Protocol deviation

Abbreviation	Term
PE	pulmonary embolism
PGA	Physician's Global Assessment
PIP	proximal interphalangeal
pJIA	polyarticular course juvenile idiopathic arthritis
PK	pharmacokinetic(s)
PMAP	population modeling analysis plan
PsA	psoriatic arthritis
RA	rheumatoid arthritis
RF+	rheumatoid factor positive
RF-	rheumatoid factor negative
RP	risk period
SAE	serious adverse event
SAP	statistical analysis plan
SAS	safety analysis set
SD	standard deviation
SI	serious infection
sJIA	systemic juvenile idiopathic arthritis
SMQ	standardised MedDRA queries
SOC	system organ class
SOP	standard operating procedure
SUN	Standard Uveitis Nomenclature
TB	tuberculosis
TE	thromboembolism
TEA	tender entheseal assessment
TEAE	treatment-emergent adverse event
TyK2	tyrosine kinase 2
ULN	upper limit of normal
US	United States
VAS	visual analog scale
VTE	venous thromboembolism
